10.4.2 Secondary Endpoints

- Change in PGA between Baseline and Week 12
- Change in the 100 mm VAS Pain Scale between Baseline and Week 12
- Use of rescue analgesia (amount of acetaminophen used between Baseline and Week 12)
- Incidence and severity of treatment-emergent adverse events (TEAEs)

A serial gatekeeping approach will be used to test the secondary endpoints in a sequential manner (i.e. PGA, 100 mm VAS, rescue analgesia).

The difference between treatment groups in the mean change in PGA from Baseline to Week 12 will be analyzed using a similar MMRM model, with Treatment assignment, Week, and Baseline value as fixed effects and including patient as a repeated measure with a compound symmetric covariance matrix for residuals.

The difference between treatment groups in the mean change in 100 mm VAS from Baseline to Week 12 will be analyzed using a similar MMRM model, with Treatment assignment, and Baseline value as fixed effects and including patient as a repeated measure with a compound symmetric covariance matrix for residuals.

The difference between treatment groups in the amount of acetaminophen used between Baseline and Week 12 will be analyzed with a Wilcoxon rank-sum test.

All secondary efficacy analyses will be reported with one sided p-values and successively compared to a critical level of 0.025 if each preceding test was significant.

10.4.3 Exploratory Endpoints

- Change in WOMAC B stiffness sub score between Baseline and Weeks 2, 4, 6, 8, 10, 12 and 24
- Response status based on the OMERACT-OARSI criteria at Weeks 2, 4, 6, 8, 10, 12 and 24
- Proportion of treatment failures at Week 12
- Change in pain and function CDF plot for Ampion and saline patients
- A Bayesian meta-analysis for LK WOMAC A pain sub score including KL 4 patients from studies AP-003-A, AP-003-B, AP-003-C, AP-004, and AP-013
- Change in WOMAC A pain sub score between Baseline and Weeks 2, 4, 6, 8, 10, and 24
- Change in PGA between Baseline and Weeks 2, 4, 6, 8, 10, and 24
- Change in WOMAC C physical function sub score between Baseline and Weeks 2, 4, 6, 8, 10, and 24
- If collected, difference in urine analysis between treatment groups at Week 12

The Bayesian meta-analysis methodology is described in the Statistical Analysis Plan.

Percent responders using the OMERACT-OARSI criteria will be analyzed using separate logistic regression models for each visit.

Proportion of treatment failures will be analyzed using Fisher's exact tests.

Analysis with exploratory biomarkers, such as those for analgesic use and chemokines and cytokines associated with inflammation and cartilage regeneration may be analyzed to compare differences between treatment groups using urine samples collected at Week 12.

All other exploratory endpoints will be analyzed as the difference between treatment groups at each time point extracted from the MMRM model, adjusted for Baseline value.

10.4.4 Subset Analyses

The two co-primary endpoints and three efficacy secondary endpoints will be re-analyzed separately for (a) ages <60, [60, 70), and ≥ 70 , (b) men and women, (c) white and other, (d) Non-Hispanic and Hispanic.

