5.1 Description of Study Visits

5.1.1 Visit -1 (Day -28 through Day 0, in-clinic): Screening

The following procedures will be performed:

- Obtain written informed consent before the start of any study specific procedure.
- Review medical history including all previous treatments for OA
- Record prior and concomitant medications including start/stop dates, indication, dose and frequency
- Record demographic data including year of birth, age, gender and race
- Measure and record height and weight
- Perform and record physical examination
- Record KL Grade from radiological assessment that is not older than 6 months prior to screening. Patient may have an x-ray at screening in order to satisfy this requirement
- Record pain in the index knee with the WOMAC Index 3.1 using both the 5-point Likert scale and the 100mm VAS scale
- Record pain in the contralateral knee with the WOMAC Index 3.1 pain subsection using both the 5-point Likert scale and the 100mm VAS scale
- Record vital signs. (Measure body temperature, systolic blood pressure [SBP], diastolic blood pressure [DBP] and pulse rate)
- Evaluate all inclusion and exclusion criteria to ensure that patients meet all inclusion criteria and none of the exclusion criteria
- Review collection instructions of daily diary pain scores with subject

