6 METHODS OF ASSESSMENT

Demographic Data

At Visit 1(Screening), patient demographic data will be collected. These include year of birth, age, gender and race.

Medical History

At Visit 1(Screening) a complete medical history, including prior interventions to the study knee, will be obtained from each patient.

Concomitant Medications

Detailed history of medications will be documented for each patient at Screening and Baseline. Concomitant medications (especially any changes in medication) will be documented for each patient at each scheduled visit.

Physical Examination and Vital signs

Height in feet and inches will be measured at Screening.

Body weight in pounds (lb) will be measured at Screening.

Body temperature (deg F) will be measured at each visit.

SBP and DBP and pulse rate will be measured with the patient in a seated position.

The full physical examination will consist of examining the following body systems: cardiovascular, respiratory, abdominal, skin and musculoskeletal other than the knee. The physical examination of the target knee will consist of evaluating the knee joint for effusion and tenderness on palpation. [Table 6.1](#) below lists the various study activities and timing.

Biomarkers

At Week 12 urine samples will be collected and may be analyzed to compare differences between treatment groups for biomarkers, such as those for analgesic use and chemokines and cytokines associated with inflammation and cartilage regeneration.

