## **8. STATISTICAL METHODS OF ANALYSIS**

### **8.1 General Principles**

Data will be summarized by saline and Ampion arms. Descriptive statistics on continuous variables will include mean, standard deviation, median, 25th and 75th percentiles, and range. Change from Baseline will include a 95% confidence interval. Categorical variables will be summarized using frequency counts and percentages. Data listings of individual patient's data will be provided.

Statistical testing for the primary endpoints of pain and function will be performed using a one-sided p-value compared to  $\alpha=0.025$ .

Other efficacy analyses will be presented with one-sided p-values. Safety analyses will be presented as two-sided.

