### **8.6 Efficacy Analyses**

All efficacy variables will be assessed at Baseline (Day 0), Week 2, Week 4, Week 6, Week 8, Week 10, Week 12, and Week 24. Differences between treatments (Ampion and saline arms) will be presented using mean differences and 95% confidence intervals. Endpoints will be compared between Ampion and saline.

For summaries based on the PP, missing data will not be estimated or carried forward in any of the descriptive analyses. For summaries based on the ITT population, estimates from the MMRM will be shown incorporating imputed missing data via the full conditional specification method with predictive mean matching.

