### 8.6.1 Primary Effectiveness Endpoints

Change in WOMAC A pain score as measured by a 5-point Likert scale, from Baseline to Week 12, will be analyzed by including change from Baseline at 2, 4, 6, 8, 10, and 12 weeks in a mixed-effects model with repeated measures (MMRM). Treatment assignment Week, the treatment\*week interaction and Baseline WOMAC pain score will be included as fixed effects. Patient ID will be included to denote repeated measures and a compound symmetric covariance matrix will be used for residuals. Least squares means and treatment difference with 95% confidence intervals will be presented.

SAS code used will follow the following format:

```
Proc mixed;
  Class PtID treatment week;
  Model delta_pain = treatment baseline_pain week treatment*week;
  Repeated week / subject=newID type = CS;
  Lsmeans active*week / SLICE=week diff;
run;
```

The primary analysis will include the repeated measures of WOMAC C function sub score from Baseline to Weeks 2, 4, 6, 8, 10, and 12 and will use a mixed-effects model with repeated measures MMRM model, with Week as a fixed effect, and including patient ID as a repeated measure with a compound symmetric covariance matrix for residuals.

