### 8.6.3 Subset analyses

The two co-primary endpoints and three secondary effectiveness endpoints will be analyzed by subsets for:

- (a) ages <60, [60, 70), and  $\geq 70$ ,
- (b) men and women,
- (c) white and other,
- (d) Non-Hispanic and Hispanic

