### **10.3 Figures**

Note that all figures, unless otherwise stated, will be line plots showing mean  $\pm$  SEM at each visit for each treatment arm.

1. WOMAC A Pain Subscale at Baseline and Week 12 [Boxplot]
2. Summary of WOMAC A Pain Subscale over Time
3. Summary of WOMAC B Stiffness Subscale over Time
4. Summary of WOMAC C Physical Function Subscale over Time
5. Summary of PGA over Time
6. Summary of Rescue Analgesia Used [stacked histogram]
7. Summary of OMERACT-OARSI responder rates over time [Bar chart]
8. Change in WOMAC A Pain Subscale from Baseline to Week 12 for subgroups [Forest plot]
9. Change in WOMAC C Function Subscale from Baseline to Week 12 for subgroups [Forest plot]

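### Subset analyses are run separately within each level with one-sided p-values and no treatment-by-subgroup contrast, so the output does not show whether the effect differs between subsets

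*Protocol*

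**What the plan says.** Protocol 10.4.4 (Subset Analyses) provides that the two co-primary and "three efficacy secondary endpoints will be re-analyzed separately for (a) ages <60" and for the remaining levels of age, sex, race and ethnicity. SAP 3.5 has the same content, and SAP 8.6.3 puts it as "The two co-primary endpoints and three secondary effectiveness endpoints will be analyzed by subsets for" the same four factors. That makes 3 + 2 + 2 + 2 = 9 levels and 5 endpoints, or 45 within-level analyses.

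On tests, SAP 8.1 says "Other efficacy analyses will be presented with one-sided p-values". SAP 8.6.1 adds that the WOMAC A and WOMAC C summary tables will carry a test of Ampion against saline at the primary and secondary time points. The planned summary tables include twenty subset tables (14.2.8 to 14.2.27), each produced for both ITT and PP.

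The only interaction in a specified model is treatment by week: "Model delta_pain = treatment baseline_pain week treatment*week" (SAP 8.6.1). No model or test contains treatment by subgroup.

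On estimates, SAP 8.6 says "Differences between treatments (Ampion and saline arms) will be presented using mean differences and 95% confidence intervals". SAP 10.3 plans subgroup forest plots for the two co-primary endpoints, but none for PGA, VAS or rescue analgesia.

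**The concern.** A test within one level asks whether the effect is distinguishable from zero in that level. The question behind a subset analysis is whether the effect differs between levels, and only a contrast between levels addresses it. The planned tables would set one-sided p-values for neighbouring levels side by side without that contrast.

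Each level holds only part of a sample sized for the whole trial. A perfectly uniform effect will therefore often reach significance in one level and miss it in the next, simply because the levels are small or unequal. Such a pattern is easily taken for a real difference by age, sex, race or ethnicity. What is at stake is the interpretation of subset results in the study report; the success criterion of the trial is not involved.

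**Working it through.** **Inputs.** Pain: mean changes -0.83 and -0.62 (difference 0.21), SD 0.85. Function: 984 patients for 90% power, with effect and SD not stated. Both are from Protocol 4.1 and SAP 2.4. Test level: one-sided 0.025 (Protocol 10.3.4). Subset shares are not in the documents, so they are assumed: equal thirds for age, and 50/50, 80/20 and 90/10 for two-level factors. The calculation treats Week 12 change as a two-sample normal comparison, 1:1 within each level, with the same true effect in every level.

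**1. The plan's own figures.** Pain, per arm: 2 × (1.960 + 1.2816)² × 0.85² / 0.21² = 344.3, rounded up to 345, or 690 in total, as stated. Pain power is 97.2% at 984 and 97.8% at 1,034; the plan states 97%.

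**2. Overall noncentrality at 984 patients.** Function: λ = 1.960 + 1.2816 ≈ 3.24 (implied effect 2λ/√984 = 0.207 SD). Pain: λ = (0.21/0.85) × √984/2 = 3.87.

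**3. Power within a level holding share f.** Power = Φ(λ√f - 1.96).

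| Share f | Function | Pain |
|---|---|---|
| 0.90 | 87% | 96% |
| 0.80 | 83% | 93% |
| 0.50 | 63% | 78% |
| 1/3 | 47% | 61% |
| 0.20 | 30% | 41% |
| 0.10 | 17% | 23% |

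**4. Chance of mixed verdicts under a uniform effect.** Two levels: p₁(1 - p₂) + p₂(1 - p₁). Three equal levels: 1 - p³ - (1 - p)³.

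- Three equal age bands, function: 1 - 0.465³ - 0.535³ ≈ 0.75. Pain: 1 - 0.609³ - 0.391³ ≈ 0.71.
- 50/50, function: 2 × 0.630 × 0.370 = 0.47. Pain: 2 × 0.782 × 0.218 = 0.34.
- 80/20: function 0.63, pain 0.58.
- 90/10, function: 0.868 × 0.825 + 0.175 × 0.132 = 0.74. Pain: 0.957 × 0.769 + 0.231 × 0.043 ≈ 0.75.

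**5. What a direct contrast could detect.** For a two-level factor with shares s and 1 - s, and an interaction as large as the overall effect, the contrast has noncentrality λ√(s(1 - s)). At two-sided 0.05:

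- 50/50: function 3.24 × 0.5 = 1.62, power 37%; pain 3.87 × 0.5 = 1.94, power 49%.
- 90/10: function 3.24 × 0.3 = 0.97, power 16%; pain 3.87 × 0.3 = 1.16, power 21%.

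**The case against.** The strongest reply is that the plan draws no conclusion from subset significance. No section sets a decision rule on it, SAP 2.2 speaks only of reporting objectives by subset, and the testing hierarchy in SAP 8.6.7 gives subsets no confirmatory role. Mean differences with 95% CIs and co-primary forest plots are already planned. All of this stands. A reader might infer that the plan judges heterogeneity by comparing within-level p-values, and that its subset results are bound to mislead; the text prescribes no such comparison. What remains is that the p-values are planned and the contrast is not.

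A second reply is that a contrast would have little power. That is correct. It argues for estimation with an interval, and it does not argue for keeping within-level tests, which answer a different question.

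Two further readings should be resisted. A reader might take the 10% chance that all three age bands are significant for WOMAC C (0.465³) and infer a 90% chance of apparent heterogeneity. That complement includes the 15% chance that no band is significant (0.535³), which is a uniform verdict; the mixed-verdict figure is about 75%. A reader might also infer that ethnicity will go unrecorded, because Protocol 5.1.1 ("Record demographic data including year of birth, age, gender and race") and Section 6 ("These include year of birth, age, gender and race") do not name it. Both lists are open-ended, and Protocol 10.3.11.1, SAP 8.3 and Listing 6 treat ethnicity as an available variable. The case report form is not among the documents, so this is an inconsistency of wording and no evidence of missing data.

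**Conclusion.** The concern holds in a limited form. The subset plan provides within-level estimates and one-sided p-values, but nothing that estimates how the effect differs between levels. With a uniform effect, 984 patients and one-sided 0.025, mixed verdicts are the likeliest outcome for three equal age bands (about 75% for function, 71% for pain). They are common for an even two-way split (47% and 34%) and about as likely as for the age bands at 90/10 (about 74% for function). These figures rest on the assumed shares, the normal approximation and the plan's own effect assumptions; an increase in sample size after the interim analysis would change them. They describe what the tables could show, and the plan does not commit anyone to reading them that way. The co-primary analysis, alpha, sample size and secondary hierarchy are untouched, so this is a worthwhile correction of modest weight.

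**What to change.** In Protocol 10.4.4 and SAP 3.5 and 8.6.3, replace separate re-analysis as follows.

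- **WOMAC A, WOMAC C, PGA and VAS:** fit one model per factor on the whole ITT set and estimate the treatment-by-subgroup contrast at Week 12. In the repeated-measures models this needs the treatment-by-week-by-subgroup term with its lower-order terms. Report the contrast and the subset estimates with 95% CIs, label them descriptive, and drop within-level p-values.
- **Rescue analgesia:** the planned Wilcoxon rank-sum test (SAP 8.6.2) has no model to carry an interaction term, so report subset differences descriptively.
- **Stated limit:** say in the SAP that the contrast has low power and that a non-significant contrast is not evidence of a uniform effect.
- **Housekeeping:** name ethnicity in the demographic lists of Protocol 5.1.1 and Section 6, in line with 10.3.11.1.

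The cost is SAP and protocol wording and a few model terms. The forest plots for the co-primary endpoints can stay as planned.

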10.4.5 Sensitivity Analysis

The two co-primary endpoints and three efficacy secondary endpoints will be re-analyzed separately in the per-protocol population to exclude treatment failures.

10.5 Missing and Spurious Data

All data collected under this study protocol will be included in the assessment of patient safety. Missing or incomplete AE data will assume greatest relationship to study drug and/or severity.

For the co-primary effectiveness analysis of WOMAC pain change and WOMAC C function change, missing change scores will be imputed when the ITT analysis population is used. Missing data will be imputed by the fully conditional specification predictive mean matching multiple imputation approach of Berglund and Heeringa (2014). A sensitivity analysis will be conducted in which the missing 12-week endpoint is replaced by the Baseline WOMAC pain score.

Per the WOMAC User Guide, the patient's response will be regarded as invalid, and the subscale(s) deficient, in the event that two pain, both stiffness, or more than four physical function items are omitted. Further, if one pain, one stiffness, or 1-3 physical function units are missing, the average value for the subscale will be substituted in lieu of the missing item value(s).

11 REGULATORY, ETHICAL AND LEGAL OBLIGATIONS

11.1 Declaration of Helsinki

The Principal Investigator will ensure that this Study is conducted in accordance with the most recent revision of the Declaration of Helsinki.

11.2 Good Clinical Practice

The Study will be conducted according to the study protocol and to Standard Operating Procedures (SOPs) that meet the guidelines provided by the International Conference on Harmonisation (ICH) for Good Clinical Practice in clinical studies.

11.3 Institutional Review Boards/Ethics Committees

Before implementing this study, the protocol, the proposed patient informed consent forms and other information for the patients, must be reviewed by a properly constituted committee or committees responsible for approving clinical studies. The IRB/IEC written, signed approval letter/form must contain approval of the designated investigator, the protocol (identifying protocol title, date and version number), and of the patient informed consent form (date, version).

Any change or addition to the protocol can only be made in a written protocol amendment that must be approved by the Sponsor, the IRB/IEC and the Health Authorities.

11.4 Regulatory Authority Approval

Before this study is implemented, the protocol must be approved by the relevant regulatory authority.

11.5 Informed Consent

The investigator must fully inform the patient of all pertinent aspects of the trial including the written information approved/favorably assessed by the IRB/IEC.

Prior to the start of the pre-study examination, the written informed consent form must be signed and personally dated by the patient and by the physician who conducted the informed consent discussion. One copy of the written information and signed consent form must be given to each patient and one copy must be retained in the investigator's study records.

11.6 Patient Confidentiality and Disclosure

Data on patients collected on eCRFs during the trial will be documented in an anonymous fashion and the patient will only be identified by the patient number, and by his/her initials. As an exception, if it is necessary for safety or regulatory reasons to identify the patient, all parties are bound to keep this information confidential.

The investigator will guarantee that all persons involved will respect the confidentiality of any information concerning the trial patients. All parties involved in the study will maintain strict confidentiality to assure that neither the person nor the family privacy of a patient participating in the trial is violated. Likewise, the appropriate measures shall be taken to prevent access of non-authorized persons to the trial data.

11.7 Collection, Monitoring and Auditing Study Documentation, and Data Storage

11.7.1 Collection of Data and Monitoring Procedures

This study will use a 21 CFR Part 11 compliant electronic data capture system (eDC). An electronic case report form (eCRF) is used for data recording. All data requested on the eCRF must be entered and all missing data must be accounted for.

The data will be checked for completeness and correctness as it is entered by the real-time online checks applied by the eDC system. Off-line checks will also be run to perform any additional data review required. Discrepancy reports will be generated accordingly and transferred to the study center for resolution by the investigator or his/her designee.

Accurate and reliable data collection will be assured by verification and cross-check of the eCRF against the investigator's records by the study monitor (source document verification), and the maintenance of a study drug-dispensing log by the investigator.

Before study initiation, at a site initiation visit or at an investigator's meeting, a Sponsor representative will review the protocol and case report forms with the investigators and their staff. During the study a monitor will visit the site regularly to check the completeness of patient records, the accuracy of entries on the case report forms, the adherence to the protocol and to Good Clinical Practice, the progress of enrollment. The monitor will ensure during on-site visits that study medication is being stored, dispensed and accounted for according to specifications. Key trial personnel must be available to assist the monitors during these visits.

The investigator must give the monitor access to relevant hospital or clinical records, to confirm their consistency with the case report form entries. No information in these records about the identity of the patients will leave the study center. Monitoring standards require full verification for the presence of informed consent, adherence to the inclusion/exclusion criteria, documentation of SAEs and the recording of primary efficacy and safety variables. Additional checks of the consistency of the source data with the eCRFs are performed according to the study-specific monitoring plan.

11.7.2 Auditing Procedure

In addition to the routine monitoring procedures the Sponsor or the regulatory authority can conduct an audit or an inspection (during the study or after its completion) to evaluate compliance with the protocol and the principles of Good Clinical Practice.

The investigator agrees that representatives of the Sponsor and Regulatory Authorities will have direct access, both during and after the course of this study, to audit and review all study-relevant medical records.

